6.5.1 Primary Safety Endpoints

- Solicited adverse events:
 - Serious/severe solicited adverse events will be summarized by group, by post-vaccination time period as well as overall (under maximum severity), and by term by post-vaccination time period as well as overall (under maximum severity), as well as listed.
- Unsolicited adverse events:
 - Serious/severe unsolicited AEs will be summarized by group, maximum causality and by class (serious vs severe) under maximum causality, by post-vaccination

time period (prior to dose 2 vs following dose 2) as well as overall, and reasons for SAE classification (wherever such subcategories are relevant), as well as by SOC and PT among serious events only (and among those serious and related), and among severe events only (and among those severe and related). These events will also be listed.

- Listings will be prepared for those subjects who died or withdrew from the study due to an AE.

Two-sided p-values from the Fisher exact test of the number of subjects with an event will be presented for:

- Severe solicited events (overall, and by event term)
- Any serious unsolicited event
- Any serious and related unsolicited event
- Any severe unsolicited event
- Any severe and related unsolicited event

These comparisons will be conducted for the following groups:

- UAM4 Groups 1 & 2 vs UAM1 Groups 1 & 2
 - Post-dose-1 and overall, TVP
- UAM4 Group 2 vs UAM1 Group 2
 - Post-dose-2, TVP subjects who received both doses
- UAM4 Groups 3 & 4 vs UAM1 Groups 1 & 2
 - Post-dose-1 and overall, TVP
- UAM4 Group 4 vs UAM1 Group 2
 - Post-dose-2, TVP subjects who received both doses
- UAM4 Group 5 vs UAM4 Group 7
 - Post-dose-1, post-dose-2, and overall, TVP
- UAM4 Group 6 vs UAM4 Group 7
 - Post-dose-1, post-dose-2, and overall, TVP

Comparisons for both solicited and unsolicited events will be conducted separately for post-dose-1 and post-dose 2, as well as following any dose. Comparisons involving post-dose-2 data will include only subjects receiving both doses.

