2. STUDY OBJECTIVES

Assessment of the general safety and immunogenicity of the 2 candidate vaccines in OPV vaccinated subjects will be primarily based on comparison with data obtained in the previously conducted Phase 4 study of Sabin mOPV2 in order to assess immunogenicity and establish an acceptable safety profile in these populations. Assessment of the general safety of the 2 candidate vaccines in IPV-only vaccinated subjects will be based on comparison with data of the placebo group.

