10.2 DETERMINATION OF SAMPLE SIZE

Groups 1 through 4:

Sample size is chosen here to mirror that of the historical control study, UAM1. The serotype 2 Day 28 seroprotection rate among OPV-vaccinated individuals is expected to be 95% for subjects receiving a single dose of either investigational vaccine or the type 2 Sabin OPV control vaccine (historical control). 77 evaluable subjects per vaccine group are required to achieve 80% power for a test of non-inferiority to the historical control with a type I error rate of $\alpha = 0.025$ and a non-inferiority margin of 10%. 45 subjects are required to have 90% probability of observing at least one occurrence of an adverse event, when the true adverse event rate is 5%. Allowing for a 10% non-evaluability/dropout rate requires 50 subjects for the safety evaluations. For each vaccine candidate, both 1- and 2-dose groups may be used to assess the Day 28 immunogenicity endpoint, providing 100 subjects for the primary immunogenicity comparison. Therefore, 50 subjects will be allocated to each dose group, to also collect adequate safety data for each group, as defined above.

Groups 5 through 7:

Due to observed transient and asymptomatic elevated values of alanine aminotransferase (ALT), aspartate aminotransferase (AST) and creatine kinase (CK) in the first-in-human phase 1 study, UAM4a, conducted in IPV-vaccinated adults in a contained environment, CK, ALT, AST, GGT, bilirubin and albumin have been designated for further evaluation in this study. Data from OPV-primed individuals in study UAM1 suggest the background rate of spurious elevations with the safe mOPV2 vaccine may be approximately 6%. If the true rate with either candidate vaccine is 4 times the expected rate, 44 subjects per group (each vaccine, plus control) would be required to have 80% power to detect a significant increase in the rate (lower one-sided 95% confidence bound for risk difference > 0) relative to the placebo group. If, upon review of interim safety data, the DSMB agrees that a) despite all reasonable efforts, recruitment has stagnated, and b) sufficient data have accrued to satisfy safety objectives relevant to these groups, group sizes can be truncated.

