3.2 Study design

This is a multicenter, partial blind, placebo-controlled, randomized study in 200 healthy OPV-vaccinated adults and in 48 to 132 healthy IPV-only vaccinated adults (age range 18 to 50 years), as follows:

- 50 OPV-vaccinated adults to receive 1 dose of nOPV2 candidate 1 (Group 1);
- 50 OPV-vaccinated adults to receive 2 doses of nOPV2 candidate 1 (Group 2), administered 28 days apart;
- 50 OPV-vaccinated adults to receive 1 dose of nOPV2 candidate 2 (Group 3);

- 50 OPV-vaccinated adults to receive 2 doses of nOPV2 candidate 2 (Group 4), administered 28 days apart;
- 16 to 44 IPV-only vaccinated adults to receive 2 doses of nOPV2 candidate 1 (Group 5), administered 28 days apart;
- 16 to 44 IPV-only vaccinated adults to receive 2 doses of nOPV2 candidate 2 (Group 6), administered 28 days apart;
- 16 to 44 IPV-only vaccinated adults to receive placebo (Group 7), administered 28 days apart.

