5.1 General Principles

The study UAM1, conducted in a pre-OPV2 cessation period (2015-2016), was specifically designed to provide active control comparator data for both safety and immunogenicity for the OPV-vaccinated adults given the novel vaccine candidates in this study. For all endpoints for OPV-vaccinated subjects, summaries of data from this study will be presented alongside corresponding summaries from UAM1. Summaries of data from IPV-vaccinated subjects will be presented according to group (each candidate, and placebo), and have no historical control companion groups. Summaries of demographics, baseline characteristics, and immunogenicity data from this study will be prepared by site and overall, to assess comparability of sites. For OPV-vaccinated subjects, comparative analyses will be limited to comparison of each vaccine to the UAM1 Sabin 2 control; for IPV-vaccinated subjects, each candidate vaccine group will be compared to the placebo group for safety endpoints.

All data will be summarized and/or listed. Unless otherwise specified in this document, a two-sided type I error rate of alpha = 0.05 will be used for inferential methods, such as for the generation of confidence intervals.

Unless otherwise specified, descriptive statistics (n, mean, median, standard deviation, minimum, maximum) will be used to describe continuous variables, and frequencies and percentages will be used to describe categorical variables.

Statistical analyses will be generated using SAS®, version 9.4 or above.

Unless otherwise specified, tables will include presentation of results by time point and by group, and overall, when possible. Figures and tables which provide more than summary statistics may include neutral explanatory text to aid in their description of the underlying data.

Unless otherwise noted, “baseline” will refer to the day of first vaccination for all participants in all groups.

To the extent possible, unintended differences in terms collected on CRFs between the two studies will be aligned for summary and presentation, with any recoding of UAM1 terms clearly specified in the study report. Coded terms will use a common coding dictionary across the two studies.

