Clinical laboratory abnormalities will be summarized by lab parameter, time point and grade (with separate categories for high and for low values of a given lab value, where relevant), as well as in a shift table displaying the frequency of post-baseline abnormalities by grade for each time point cross-tabulated with the classification at baseline, for each time point for each lab parameter, maximum grade across lab parameter within each time point, and maximum grade across post-baseline time points and lab parameter. A separate table will summarize according to grade only those values considered to be clinically relevant. Additional summary tables will be produced including the continuous values and the change from baseline for each group and post-vaccination day. Boxplots will display the raw value by lab parameter and study collection day, and will include separate symbols to depict values out of range and those out of range and clinically relevant. A listing, including grade and clinical relevance, will also be prepared.

While all safety lab abnormalities will be summarized, for each of the specific safety lab parameters listed below, the rate of moderate or greater post-baseline abnormalities will be presented at the subject level overall as well as by timepoint, and by abnormality grade (using the maximum grade post-baseline, where relevant), and accompanied by a two-sided 90% confidence interval using the Miettinen and Nurminen method for the risk difference of each vaccine candidate vs. the comparator group: ALT, AST, CK, GGT, bilirubin and albumin. For IPV-vaccinated subjects (Groups 5 and 6), comparisons will be made relative to the placebo

group (Group 7), and for OPV-vaccinated subjects (Groups 1 – 4), comparisons will be made relative to the corresponding UAM1 control (for lab values assessed in both studies), combining groups where possible, as described above (e.g., Group 1 & 2, post-dose-1).

Pregnancy test results will be listed.

Abnormal vital signs (heart rate, systolic/diastolic blood pressure, body temperature) will be summarized by group and by time point (day, prior to/following vaccination). The summary will also include the number and percent of subjects with abnormal and clinically relevant vital signs. Vital signs will be listed, and summarized as continuous variables by time point, including change from baseline, by group, and change pre- to post-vaccination for vaccination visits.

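### SAP 6.5.1 compares SAEs and severe AEs between groups by Fisher p-values alone; a risk difference with a confidence interval should be added

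*SAP*

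**What the plan says.** Two of the three primary objectives are safety comparisons on SAEs and severe AEs: each candidate against the UAM1 Sabin control in OPV-vaccinated adults, and each candidate against placebo in IPV-only adults. For the OPV comparison, Protocol Section 2 gives the aim as to "establish an acceptable safety profile in these populations".

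- **SAP 6.5.1 (primary safety).** After the by-group summaries and listings, the between-group element is: "Two-sided p-values from the Fisher exact test of the number of subjects with an event will be presented for" severe solicited events and four classes of serious or severe unsolicited events. Groups 1 & 2 and Groups 3 & 4 are compared with UAM1, and Groups 5 and 6 with Group 7, by dose period and overall. No risk difference or interval for a difference appears, and no threshold of its own is set. The SAP 5.1 default is that "a two-sided type I error rate of alpha = 0.05 will be used for inferential methods".
- **SAP 6.5 (general).** AE summaries show each group's number and percentage, with an exact 95% interval for that proportion.
- **SAP 6.5.2 (secondary safety).** For ALT, AST, CK, GGT, bilirubin and albumin, the rates are "accompanied by a two-sided 90% confidence interval using the Miettinen and Nurminen method for the risk difference", against placebo for IPV groups and against UAM1 for OPV groups where the parameter was measured in both studies.
- **Group sizes.** SAP 3.2 has "16 to 44 IPV-only vaccinated adults to receive placebo (Group 7), administered 28 days apart", with the same range for Groups 5 and 6.
- **Protocol 10.1.4.** Safety is analysed descriptively, and the comparison with the historical control rests on descriptive statistics. SAP Section 7 lists only antibody fold rise as a difference from the protocol.

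**The concern.** A p-value does not say how large an excess the data are compatible with. In groups of 16 to 44, a non-significant Fisher test is a likely result even under a sizeable true increase, and the planned output would not show what has been ruled out. The exact intervals in SAP 6.5 bound each group's own rate, so they do not answer the comparative question in the objectives. The more informative method is already in the SAP, but it is applied to secondary laboratory endpoints and not to the primary ones. At stake is how well the report can support a statement about relative safety.

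**Working it through.** **1. The plan's own calculation.** Protocol 10.2 says the "background rate of spurious elevations with the safe mOPV2 vaccine may be approximately 6" per cent. It continues: "If the true rate with either candidate vaccine is 4 times the expected rate, 44 subjects per group" "would be required to have 80% power to detect a significant increase in the rate", judged by a lower one-sided 95% bound for the risk difference above 0. So the rates are 6% and 4 × 6% = 24%. Exact binomial enumeration of that criterion (lower limit of the 90% Miettinen-Nurminen interval above 0) at 44 vs 44 gives power 79.7%. The stated 80% is reproduced. It applies to laboratory elevations and to that one-sided criterion.

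**2. Same rates under the SAP 6.5.1 test.** The share of non-significant trials is the sum, over all tables (x₁, x₀) with two-sided Fisher p > 0.05, of Bin(x₁; n, 0.24) × Bin(x₀; n, 0.06). Using 6% for SAEs or severe AEs is an assumption, since the documents give no background rate for them. The placebo recipients from both enrolment stages form one Group 7, so equal group sizes are used. No dropout is applied.

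| Comparison | n per group | Non-significant, 24% vs 6% |
|---|---|---|
| Candidate vs placebo, minimum | 16 | 85.0% |
| Candidate vs placebo, maximum | 44 | 42.2% |
| 2-dose group vs UAM1 Group 2, post-dose 2 | 50 | 36.7% |
| Pooled groups vs pooled UAM1 | 100 | 5.5% |

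**3. Sensitivity to the borrowed rate.** Non-significant share for a fourfold increase from other assumed backgrounds:

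| Background | 16 vs 16 | 44 vs 44 | 100 vs 100 |
|---|---|---|---|
| 1% | about 100% | 99.5% | 90.4% |
| 2% | 99.5% | 93.4% | 62.8% |
| 3% | 97.8% | 81.3% | 38.8% |
| 5% | 90.1% | 53.4% | 11.7% |
| 10% | 64.1% | 12.1% | 0.1% |

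**4. What an interval would add.** With x vaccine events and none on placebo (n each), the two-sided Fisher p is 2·C(n,x)/C(2n,x).

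- 4/16 vs 0/16: p = 2 × 1820/35960 = 0.10. The 95% Miettinen-Nurminen interval is +2.7 to +49.9 points.
- 5/44 vs 0/44: p = 0.055; interval +2.8 to +24.1 points.
- 4/16 vs 1/16: p = 0.33; difference 18.8 points, interval −8.2 to +45.2.
- 0/16 vs 0/16: p = 1. With no events the upper limit is k/(1+k), where k = z²N/[n(N−1)]. Here k = 3.84 × 32/(16 × 31) = 0.248, giving +19.9 points.
- 0/44 vs 0/44: k = 3.84 × 88/(44 × 87) = 0.088, giving +8.1 points.

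Against zero placebo events, Fisher needs at least 5/16 (p = 0.043) or 6/44 (p = 0.026) to reach 0.05.

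**5. What an interval does not add.** Under 24% vs 6%, the lower limit of the 95% Miettinen-Nurminen interval still fails to exceed 0 in 72.6% of trials at 16 per group and 30.4% at 44. With a 90% interval the figures are 57.1% and 20.3%.

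**The case against.** The strongest reply is that SAP 6.5.1 does not stand alone. Counts, percentages and exact 95% intervals are required for each group, OPV results are set beside UAM1, and events are broken down and listed. Any reader can derive the difference from these. In the case of no events, the exact upper limit for 0/16 is 1 − 0.025^(1/16) = 20.6%, which warns of much the same uncertainty as the +19.9 points above. Protocol 11.2 also records laboratory values above grade 1 as AEs, so severe ones can enter the primary endpoint and are partly covered by the SAP 6.5.2 intervals. All of this stands. It would therefore be wrong to call the p-values the only comparative evidence: they are the only *between-group statistic* specified. Solicited events and clinical unsolicited events still have no interval for the difference.

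A reader might infer that the sponsor will treat p > 0.05 as proof of safety. Neither document says so; SAP 6.5.1 says only that p-values will be presented. A reader might also attach the acceptable-profile aim to the placebo comparison. In Protocol Section 2 it belongs to the OPV comparison with the Sabin study, where the illustrative miss rate is 5.5% for pooled groups.

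The Section 7 omission is minor. Protocol 10.1 leaves methods to the SAP, 10.1.2 foresees tests at a two-sided 5% level, and the explicit descriptive wording for comparisons concerns the historical control.

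**Conclusion.** The point holds as a reporting weakness. The primary safety endpoints are compared between groups by two-sided Fisher p-values, with no risk difference and no interval for the excess, although the SAP already specifies such an interval for six laboratory parameters.

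The 42% to 85% range illustrates how little a non-significant result would say in the placebo comparisons. It depends on the borrowed 6% laboratory rate, a fourfold increase, and 44 or 16 per group. Rarer events would give higher shares and commoner ones lower. It should not be read as the power for SAEs or severe AEs, or as applying to the pooled UAM1 comparison. Nor does it show that the test is the main cause: much of the miss rate is sample size, as step 5 of the check shows. The gain from the change is a visible statement of what excess has and has not been excluded.

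**What to change.** - In SAP 6.5.1, for every listed event class and group pair, report the risk difference with a two-sided 95% Miettinen-Nurminen interval as the main between-group result. Keep the Fisher p-value as secondary.
- Add a sentence such as: *Safety conclusions will rest on the estimated difference and its upper confidence limit; a non-significant p-value will not be taken as evidence of no increase.*
- List the added Fisher tests in SAP Section 7.

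The cost is SAP wording and one extra table column, using a method already specified in SAP 6.5.2. No extra subjects or data are needed. The downside is that wide limits at 16 per group will be plain in the report. Power is unchanged.
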